5.4 Temporal Artery Temperature Measurement and Fever Assessments

Participants' temperatures will be taken using a digital temporal artery thermometer that will be provided to each parent/LAR during enrollment to use for the study and keep for use following the study. The initial temperature will be recorded in the clinic and study staff will demonstrate proper use of the thermometer to the parent. Temperatures will be collected during both Visit 1 and Visit 2. Thereafter, parent(s)/LAR(s) will measure and record the participant's temperature at approximately the same time each day (preferably after 6:00 PM or right before participant goes to bed) beginning on Day 1 (day of vaccination) and will do so through Day 8 following Visits 1 and 2. In addition, parents will be instructed to take a temperature using a temporal artery thermometer if their child feels warm or feverish at any time from Days 1-8 after Visit 1 and 2 and to record the temperature on the memory aid. Temperature measurements will be done for both the simultaneous and sequential groups in a similar fashion such that those children in the simultaneous group, who do not receive vaccinations at Visit 2, will also have temperatures measured. If at any time a temperature $\geq 100.4^{\circ}\text{F}$ ($\geq 38^{\circ}\text{C}$) or $\leq 95^{\circ}\text{F}$ ($\leq 35^{\circ}\text{F}$) is recorded, a second measurement will be taken within 20 minutes. The highest of those two temperature measurements will be recorded. If more than one temperature is taken on the same day (prior to bedtime), the highest temperature for that day should be recorded on either the paper memory aid or entered into REDCap. Any temperature measured after your child's bedtime memory aid entry has been completed, should be considered for the next day's memory aid entry.

All temperatures will be measured using a temporal artery thermometer (Exergen Medical Scanner Model TAT-2000C)^{18,19}. Although parents may elect to use an alternate method for measuring temperatures, they will be required to measure temporal artery temperature measurements as specified above.

For this study, temperatures will be documented using either the electronic memory aid through REDCap or the paper memory aid. The preferred method for documentation in this study is REDCap. All parent(s)/LAR(s) will be encouraged to use the paper memory

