6.2.5 Exploratory Objectives

For exploratory objective 1 the average peak temperature on day 1 and/or 2 following Visit 1, Visit 2 and Visit 1 and 2 combined will be presented by simultaneous and sequential vaccination groups. To evaluate the duration of fever, the number of fever degree-days on day 1 or 2 following Visit 1, Visit 2 and Visit 1 and 2 combined will be presented by simultaneous and sequential vaccination groups. Comparisons will be made using a Mann-Whitney U/Wilcoxon rank-sum test.

For exploratory objective 2 we will present the use of antipyretics for fever on day 1 and/or day 2 after Visit 1 and Visit 2 (separately and combined) in the simultaneous versus sequential group in tables for presentation. The proportion of children with antipyretic use on day 1 and/or day 2 following Visit 1, Visit 2 and Visit 1 and 2 combined will be compared using a Mantel-Haenszel statistic in a stratified analysis by site between the simultaneous and sequential vaccination groups.

Exploratory objective 3 that evaluates the level of severity of fever at various time points, will be presented and compared using a Mantel-Haenszel statistic in a stratified analysis by site.

Exploratory objectives 4 and 5 evaluate fever on days 3-8 and the clinical importance of fever on days 3-8, respectively. We will present and compare the proportions in

objectives 4 and 5 using a Mantel-Haenszel statistic in a stratified analysis by site to control for the randomization blocks. We will adjust for MMR and MMRV receipt at Visit 1 if necessary when analyzing the following outcome measures- EOM5.1, EOM5.2, and EOM 5.3 due to the possibility that a measles-containing vaccine may be administered at Visit 1 to infants in both the simultaneous and sequential group. Also for objective 5, we will present and compare the mean duration of any fever starting on days 3-8 using a Mann-Whitney U/Wilcoxon rank-sum test. Other analysis to further evaluate the clinical importance of fever onset 3-8 days after Visit 1 and/or Visit 2 will be performed if necessary.

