3.2 Secondary

- a)
 - 1. SOM 1.1: Proportion of children with fever (temperature $\geq 38.0^{\circ}\text{C}$ or $\geq 100.4^{\circ}\text{F}$) on day 1 and/or day 2 following Visit 1.
 - 2. SOM 1.2: Proportion of children with fever (temperature $\geq 38.0^{\circ}\text{C}$ or $\geq 100.4^{\circ}\text{F}$) on day 1 and/or day 2 following Visit 2.
- b)
 - 1. SOM 2.1: Proportions of children with moderate/severe fever (GRADE 2 and/or 3) on day 1 and/or day 2 following Visit 1, Visit 2, and Visit 1 and Visit 2 combined.
 - 2. SOM 2.2: Average number of consecutive days of fever (temperature $\geq 38.0^{\circ}\text{C}$ or $\geq 100.4^{\circ}\text{F}$) per subject for fever starting on day 1 or 2 following Visit 1, Visit 2 and Visit 1 and Visit 2 combined. Note: fever starting on day 1 or 2 could continue through day 8.
 - 3. SOM 2.3: Proportion of children with medical care utilization (telephone call, medical office visit, emergency department visit, or hospital admission) for fever on day 1 and/or day 2 following Visit 1, Visit 2 and Visit 1 and Visit 2 combined.

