4.2 Sample Size and Power

Allowing for a 10% drop out rate given an initial N=280, there should be approximately 252 children enrolled into the study. If the true proportion of children who have fever on day 1 and/or day 2 after the first and/or second visit in the simultaneous group is 36% and the true proportion in the sequential group is 18%, then there is 90% power to reject the null hypothesis of no difference with N=126 per group with a two-sided alpha 0.05 level. This is based upon using a Mantel-Haenszel statistic in a stratified analysis to control for sites.

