office visit, emergency department visit or hospital admission) on day 1 and/or day 2 following Visit 1, Visit 2 and Visit 1 and 2 combined. Medical utilization for fever will be counted as positive for this analysis if onset of fever on day 1 and/or day 2 plus medical utilization on day 1, day 2 or day 3 after fever. Medical care related to fever will be determined by report on the diary.

Proportions will be compared between the simultaneous and the sequential vaccination groups using a Mantel-Haenszal statistic (three tests) in a stratified analysis by site to control for the randomization blocks. The duration of fever will be compared between groups using a Mann-Whitney U/Wilcoxon rank-sum test (three tests).

No adjustments will be made to the alpha level (two-sided alpha=0.05) for these secondary objectives.

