- d) The fourth exploratory objective (EO 4) is to compare the proportions of children with fever on at least one day during days 3-8 after Visit 1 and Visit 2 (separately and combined) in the simultaneous versus sequential group. This information is captured on the memory aid form in the REDCap database. There will be three statistical comparisons performed at the alpha 0.05 level. These group comparisons will be made using a Mantel-Haenszel statistic in a stratified analysis by site to control for the randomization blocks.
- e) The fifth exploratory objective (EO 5) is to compare the clinical importance of fever occurring on at least one day during days 3-8 after Visit 1 and Visit 2 (separately and combined) in the simultaneous versus sequential group. Clinical importance is assessed based on severity of fever, duration of fever, and medical care utilization for fever. This information is captured on the memory aid form in the REDCap database.

1. Severity of fever: To evaluate the severity of fever, the proportions of children with moderate/severe fever (GRADE 2 and/or 3 see Table 2 above) on at least one day during days 3-8 following Visit 1, Visit 2, and Visit 1 and Visit 2 combined will be presented in a tabular format. This group comparison will be made using a Mantel-Haenszel statistic in a stratified analysis by site to control for the randomization blocks.
2. Duration of fever: To evaluate the duration of fever, the average number of consecutive days of fever (temperature $\geq 38.0^{\circ}\text{C}$ or $\geq 100.4^{\circ}\text{F}$) per subject for fever starting on day 3-8 following Visit 1, Visit 2, and Visit 1 and Visit 2 combined will be calculated. A fever starting on day 3-8 could continue through day 8. The mean duration of any fever will be presented in days for children with fever that began on days 3-8 after Visit 1 and Visit 2 (separately and combined). Each consecutive day of fever on the memory aid will be counted per child per visit. Thus, a child could contribute a maximum of 6 days per study visit, should a fever be reported at each day on the memory aid. The longest duration of any fever occurring for a child will be counted for that child. e.g. If a child has fever on days 3 and 4, no fever on day 5, and fever occurring on days 6, 7, and 8 the duration of fever will be counted as 3 days for that child.

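### Apart from duration, the day 3-8 fever measures set no onset rule, so day 1-2 fevers still running on day 3 enter the late-window comparisons

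*Combined protocol and SAP*

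**What the plan says.** **Any-day rule.** For EO 4 (EOM 4.1-4.3), SAP 8.3 d) will "compare the proportions of children with fever on at least one day during days 3-8 after Visit 1 and Visit 2 (separately and combined"). Nothing is said about when the fever began. EOM 5.1 counts any Grade 2 or 3 day in the same window, and EOM 3.2 grades fever on those days, also without an onset condition. EOM 5.3 counts care for fever on days 3-8, without making clear whether the care or the fever must fall in the window.

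**Onset rule.** Duration in the same objective, EOM 5.2, is computed "for fever starting on day 3-8 following Visit 1, Visit 2, and Visit 1 and Visit 2 combined will be calculated". The day 1-2 measures also use onset. SOM 2.2 notes that "fever starting on day 1 or 2 could continue through day 8". SOM 2.3 counts care "if onset of fever on day 1 and/or day 2 plus medical utilization on day 1, day 2 or day 3 after fever" (SAP 8.2 b) 3).

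**Related text.** Protocol 6.2.5 ends its account of objectives 4 and 5 by allowing other analyses of the "clinical importance of fever onset 3-8 days after Visit 1 and/or Visit 2", if needed. The SAP does not carry this over. Protocol 5.4 says that a temperature taken after the child's "bedtime memory aid entry has been completed, should be considered for the next" day's entry.

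**The concern.** A child febrile on days 2 and 3 is positive in POM 1.1 and again in EO 4. Within EO 5, severity and possibly care describe any fever present on days 3-8, while duration describes only fever that began then. The three components of clinical importance therefore refer to different sets of fevers.

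The trial expects the arms to differ in day 1-2 fever. If they do, they also differ in the number of fevers able to last into day 3. The day 3-8 comparisons can then differ between arms when new late fever is equal, and a reader could take that as a separate delayed effect of the schedule. The direction depends on the visit. After Visit 1 the simultaneous arm has had the additional vaccine. At Visit 2 only the sequential arm is vaccinated.

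Nothing else in the plan separates the two kinds of fever. The day-3 sensitivity analysis in SAP 9 applies to the primary objective only, and SAP 8.4 deals only with imbalance in MMR or MMRV receipt. Each EO 4 comparison is tested at two-sided 0.05 without adjustment.

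**Working it through.** **The plan's own figure.** SAP 4.2 states "90% power to reject the null hypothesis of no difference with N=126 per group with a two-sided alpha 0.05 level", where the true proportion in the "simultaneous group is 36% and the true proportion in the sequential group is 18"%. With a pooled z-test the null standard error is √(2 × 0.27 × 0.73 / 126) = 0.0559 and the alternative is √((0.36 × 0.64 + 0.18 × 0.82) / 126) = 0.0548. Power = Φ((0.18 − 1.96 × 0.0559) / 0.0548) = 90.1%. The figure reproduces. The documents give no figure for the day 3-8 endpoints.

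**Inputs for the carry-over**
- p, day 1-2 fever. Both visits: 36% v 18% (SAP 4.2).
- p at Visit 1: 36% v 9.5%. This places all of the simultaneous arm's 36% at Visit 1 and uses the PCV13-alone rate in Protocol 1.1 as a proxy for PCV13 with DTaP.
- p at Visit 2: 0% v 7.5%. No vaccine fever in the unvaccinated arm; the IIV3-alone rate in Protocol 1.1 for the sequential arm.
- q, share of day 1-2 fevers still present at the day-3 entry: **assumed** 10-30%.
- b, new-onset day 3-8 fever, equal in both arms: **assumed**, 10% in the table and varied below.

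**Formula.** Treating carry-over and new fever as independent, P(any febrile day on days 3-8) = b + (1 − b) × p × q.

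Example, both visits, b = 10%, q = 30%: simultaneous 0.10 + 0.90 × 0.36 × 0.30 = 0.197; sequential 0.10 + 0.90 × 0.18 × 0.30 = 0.149; RR 1.33.

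Results at b = 10%, with the chance of p < 0.05 from a two-sided pooled z-test, 126 per arm:

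| Measure | q | Simultaneous v sequential | RR | P(p < 0.05) |
|---|---|---|---|---|
| Visit 1 | 10% | 13.2% v 10.9% | 1.22 | 9% |
| Visit 1 | 20% | 16.5% v 11.7% | 1.41 | 19% |
| Visit 1 | 30% | 19.7% v 12.6% | 1.57 | 34% |
| Combined | 10% | 13.2% v 11.6% | 1.14 | 7% |
| Combined | 20% | 16.5% v 13.2% | 1.24 | 11% |
| Combined | 30% | 19.7% v 14.9% | 1.33 | 17.5% |
| Visit 2 | 10% | 10.0% v 10.7% | 0.94 | 5% |
| Visit 2 | 20% | 10.0% v 11.4% | 0.88 | 6% |
| Visit 2 | 30% | 10.0% v 12.0% | 0.83 | 8% |

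**Ranges over b = 5-15% and q = 10-30%.** Visit 1: +2.3 to +7.6 points, P(p < 0.05) 8-47%. Combined: +1.5 to +5.1 points, 6-23%. Visit 2: −0.6 to −2.1 points, 5-11%.

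**Combined visits with b widened to 20%.** The lowest RR is at b = 20%, q = 10%: 0.2288 / 0.2144 = 1.07. The highest is at b = 5%, q = 30%: 0.1526 / 0.1013 = 1.51. The excess is 0.0144 × 126 = 1.8 to 0.0513 × 126 = 6.5 children per arm.

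**With an onset rule** the p × q term drops out. With equal b the expected difference is 0 and the rejection rate returns to 5%, apart from the diary shift taken up under the fix.

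**The case against.** The strongest defence is that the definitions match the objectives. EO 4 asks about fever in days 3-8 and EO 5 about fever occurring then. Fever that a schedule causes and that lasts to day 3 is a real randomised difference in that window. Being positive in both POM 1.1 and EO 4 is no error, because nothing adds the two. All of this stands: the any-day proportion is legitimate, and what it lacks is the ability to separate new from continuing fever.

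Carry-over would also be partly visible, since SOM 2.2 follows day 1-2 fevers through day 8 and EOM 5.2 is based on onset. That stands too, but neither supplies an onset-based proportion for EO 4 or the severity part of EO 5.

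Several stronger readings are tempting but not supported:
- *Carry-over always inflates the simultaneous arm.* At Visit 2 that arm receives no vaccine, so in EOM 4.2 and the Visit 2 parts of EOM 3.2, 5.1 and 5.3 the extra fever falls in the sequential arm.
- *The protocol defines the question as onset.* In Protocol 6.2.5 that word appears only in a sentence on optional further analysis.
- *Care is certainly counted twice.* Day-3 care for a day-2 fever counts in SOM 2.3, but the wording of EOM 5.3 leaves open whether it counts there as well.
- *A planned estimate of a measles-vaccine effect is contaminated.* SAP 8.4 plans only a split by MMR/MMRV receipt, and only if receipt is imbalanced.

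**Conclusion.** The point holds as a limit on interpretation. EOM 3.2, 4.1-4.3 and 5.1, and EOM 5.3 on one reading, combine new late fever with day 1-2 fever that has not resolved, and the components of EO 5 do not share one rule. Under the trial's hypothesis the push is toward the simultaneous arm for Visit 1 and combined visits, and toward the sequential arm, by less, for Visit 2.

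The size is conditional. Persistence and background rates are assumptions. Protocol 1.1 says only that most such fever is mild and settles within a few days, which allows some to last to day 3 but gives no rate. On the assumed ranges the combined-visit RR is about 1.07 to 1.51 with no difference in new-onset late fever. A reader might infer that a false late-fever finding is likely, or that the main result is at risk. Neither follows: for combined visits the rejection probability is 6-23% on those assumptions, the endpoints are exploratory, and the primary comparison and its 90% power are unaffected.

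**What to change.** For EOM 3.2, 4.1-4.3, 5.1 and 5.3, add an analysis of fever with onset on days 3-8: a febrile entry in that window that does not continue a run of consecutive febrile days begun on day 1 or 2. This is the onset principle of EOM 5.2, and it fits the consecutive-day example in SAP 8.2 b) 2. Keep all children in the denominator. Count care in EOM 5.3 only when it follows such a fever, which also settles the ambiguity in its wording. Report the any-day version beside the onset version. Include EOM 3.2, so that the SAP does not give two unexplained day 3-8 fever counts for the same visit.

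State the remaining limit. Under Protocol 5.4 a reading taken after the day-2 bedtime entry is logged as day 3, so a fever first measured then will still be classed as day-3 onset.

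The cost is SAP wording and a few lines of derivation code on daily temperatures already collected. The downside is slightly fewer day 3-8 events in the onset version.

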8.4 Potential Adjustments to Exploratory Objectives

- a) It might be necessary to adjust for MMR and MMRV receipt at Visit 1 for the following outcome measures: EOM 3.2, EOM 3.3, EOM 4.1, EOM 4.3, EOM 5.1 and EOM 5.2. This is due to the possibility that a measles-containing vaccine may be administered at Visit 1 to infants in both the simultaneous and sequential group. If there is an imbalance (detected by a Mantel-Haenszel statistic in a stratified analysis by site) between the vaccination groups in the percentages of MMR and/or MMRV receipt at Visit 1, the aforementioned exploratory outcome measures will be evaluated by subgroups of those with MMR and/or MMRV receipt at Visit 1 and those without MMR and/or MMRV receipt at Visit 1.

9 SENSITIVITY ANALYSES

Sensitivity analyses will be performed under three conditions:

- to exclude those who received antipyretics on day 1 and/or day 2 following Visit 1 and/or Visit 2.
- to extend the risk window for fever to day 3 after Visit 1 and Visit 2.
- to compare the effect of the first versus second dose of current seasonal influenza vaccine

These sensitivity analyses will be performed for the primary objective in both study populations (ITT and Per Protocol). The statistical comparison will be made using a Mantel-Haenszel statistic in a stratified analysis by site to control for the randomization blocks. No adjustments will be made to the alpha level (two-sided $\alpha=0.05$) for these sensitivity analyses.

Appendix 1

Major Protocol Violations

Study Title: A Prospective, Randomized, Open-label Clinical Trial to Assess Fever Following Simultaneous versus Sequential Administration of 13-valent Conjugate Pneumococcal Vaccine, Diphtheria Toxoid, Tetanus Toxoid, and Acellular Pertussis Vaccine and Inactivated Influenza Vaccine in Young Children

Short Title: Fever after Simultaneous versus Sequential Vaccination in Young Children

Sponsor: Centers for Disease Control and Prevention Clinical Immunization Safety Assessment (CISA) Project

Lead Site Principal Investigator: [name], MPH

Contributing Site Principal Investigator: [name]

Centers for Disease Control and Prevention (CDC) Principal Investigator: [name]

CDC Sub-principal Investigator: [name]

NCT #: 03165981

Purpose: To define major protocol violations that will be used to establish the Per Protocol Population for the Fever after Simultaneous versus Sequential Vaccination in Young Children study

Background: Per the protocol analysis plan there will be two study populations, the Intent-to-Treat (ITT) and Per Protocol populations. The ITT Population includes any participant that was enrolled, randomized into the study, and received at least one study vaccine at Visit 1. The Per Protocol Population is a subset of the ITT Population excluding those participants who do not provide valid temperature data on days 1 and 2 following Visit 1 and Visit 2 and those with major protocol violations as determined by the study investigators. Statistical analyses will be performed for both study populations, or the ITT Population only if no participants are excluded from the Per Protocol Population.

This document stands to serve as a general guideline for the study investigators to a priori define major protocol violations. Participants with major protocol violations will not be included in the Per Protocol Population.

Major Protocol Violations Defined:

1) Inclusion/Exclusion Criteria Violations

Did Not Meet Study Inclusion Criteria	At Study Entry Visit 1	During Period of Enrollment¹
1. 12 through 16 months of age (i.e. from the 1-year birthday until the day before 17 months of age) at the time of vaccination	X	X
2. Stable health as determined by investigator's clinical examination and assessment of child's medical history	X	
3. Has received all immunizations recommended by Advisory Committee for Immunization Practices (ACIP) during the first year of life with the exception of rotavirus and influenza vaccines.* *Immunizations recommended during the first year of life include: 3 doses of DTaP, 3 doses of PCV13, 2- 3 doses of inactivated polio virus vaccine, 3 doses of Hepatitis B vaccine, and 2 or 3 doses of Hib vaccine such that the primary Hib series is complete depending upon the brand used. (https://www.cdc.gov/vaccines/schedules/hcp/imz/child-adolescent.html).	X	X
4. The parent(s)/ legally authorized representative(s) LAR(s) intend for the child to receive DTaP and PCV13 in addition to this season's IIV	X	
5. The parent(s)/LAR(s) must be willing and capable of providing permission for their child to participate through the written informed consent process	X	
6. The parent(s)/LAR(s) must be able to comply with the requirements of the protocol (e.g., completion of the memory aid (either electronic or paper diary), return for follow-up visits, respects intervals between the visits and have telephone access.	X	
7. The parent(s)/LAR(s) must be English speaking	X	
8. The parent(s)/LAR(s) must agree to sign a medical release for the child so that study personnel may obtain medical information about the child's health (if needed)	X	
Met Exclusion Criteria		
1. History of any seizure (including febrile seizure) in the child or a febrile seizure in a first degree relative* *First degree relatives include biological parents or siblings	X	X
2. Has already completed influenza vaccination during the current season per ACIP recommendations* *Children needing two doses of influenza vaccine per ACIP recommendations and who are receiving a second dose of	X	X

influenza vaccine may be enrolled; however, an attempt will be made to preferentially enroll children needing two doses at the time of receipt of their first dose of influenza vaccine		
3. Receipt of more than 3 previous doses of DTaP	X	X
4. Received the 3 rd dose of DTaP within 6 months of Visit 1	X	X
5. Receipt of more than 3 previous doses of PCV13	X	X
6. Received the 3 rd dose of PCV13 within 8 weeks of Visit 1	X	X
7. History of a severe allergic reaction (e.g. anaphylaxis) to a previous dose of any influenza, diphtheria toxoid-, tetanus toxoid-, or pertussis-containing vaccine, or pneumococcal vaccine	X	
8. History of a severe allergic reaction (e.g., anaphylaxis) to any component (including egg protein) of any of the three vaccines used in this study.	X	
9. History of Guillain-Barré syndrome within 6 weeks following a prior dose of influenza, DTaP, or tetanus toxoid containing vaccine	X	
10. History of a progressive neurologic disorder	X	
11. History of encephalopathy within 7 days of a previous pertussis-containing vaccine	X	
12. History of collapse within 3 days after a prior dose of DTaP	X	
13. Received any other licensed vaccines within 14 days (for inactivated vaccines) or 28 days (for live vaccines) prior to Visit 1* *Concomitant vaccine administration for ACIP recommended vaccines are allowed to be administered on the first vaccination day in this study but at no other time in this study period unless deemed a personal or public health priority by the health care provider caring for this patient or the study team.	X	X
14. Received an experimental/investigational agent (vaccine, drug, biologic, device, blood product, or medication) within 28 days prior to Visit 1, or expects to receive an experimental/investigational agent during the study period (up to 8 days after visit 2)	X	X
15. A moderate to severe acute illness within 72 hours of Visit 1* *All vaccines can be administered to persons with a minor illness such as diarrhea, mild upper respiratory infection without fever.	X	X
16. A reported temperature greater than or equal to 100.4°F (38.0°C) within 72 hours prior enrollment or a temperature (measured by temporal artery thermometer) greater than or equal to 100.4°F (38.0°C) at the time of enrollment* *This may result in a temporary delay of vaccination	X	X
17. Receipt of an antipyretic medication (acetaminophen or ibuprofen) within 24 hours prior to enrollment* *This may result in a temporary delay of vaccination	X	X
18. Parent(s)/LAR is planning to administer a prophylactic antipyretic or medication on the day of, and/or within 7 days following Visit 1 or Visit 2* *This exclusion does not apply if the caretaker indicates he/she might administer antipyretics or analgesics after vaccination to reduce fever or pain	X	
19. Long term (at least 14 consecutive days) oral corticosteroids (prednisone 2 mg/kg/day or equivalent other glucocorticoid), any parenteral steroids, high-dose inhaled steroids (>800 mcg/day of beclomethasone)	X	X

dipropionate or equivalent) or other immune-modifying drugs or immunosuppressants within the preceding 6 months prior to Visit 1* *Topical and nasal steroids are allowed		
20. Any confirmed or suspected immunosuppressive or immunodeficient condition, based on medical history and or their provider's routine physical examination* *No laboratory testing required	X	X
21. Has an active neoplastic disease, a history of any hematologic malignancy, current bleeding disorder, or taking anticoagulants.	X	X
22. Unable to receive an intramuscular injection in the thigh* * For example – a broken bone or cast for treatment of broken bone in a lower extremity, congenital anomaly in lower extremity precluding administration in the affected extremity or if deemed inappropriate by the study investigator	X	
23. Any condition deemed by the investigator to place the child at increased risk as a result of their participation in the study	X	
24. Any child or grandchild of a study investigator or study team member	X	X

If study team during the period of enrollment subsequent to Visit 1 becomes aware subject did not meet inclusion criteria or met exclusion meets the definition of a major violation

Met Study Exclusion Criteria	At Visit 2	After Visit 2 During Period of Enrollment²
1. Has already completed influenza vaccination during the current season per ACIP recommendations	X	X
2. History of a severe allergic reaction (e.g. anaphylaxis) to a previous dose of any influenza vaccine.	X	
3. History of a severe allergic reaction (e.g., anaphylaxis) to any component (including egg protein) of the influenza vaccine used in this study	X	
4. History of Guillain-Barré syndrome within 6 weeks following a prior dose of any influenza vaccine	X	
5. Received an experimental/investigational agent (vaccine, drug, biologic, device, blood product, or medication) after randomization or expects to receive an experimental/investigational agent during the remaining study period (up to 8 days after visit 2)	X	X
6. A moderate to severe acute illness within 24 hours of Visit 2* * This may result in a temporary delay of Visit 2 and/or vaccination. All vaccines can be administered to persons with a minor illness such as diarrhea, mild upper respiratory infection without fever.	X	X
7. A reported temperature greater than or equal to 100.4°F (38.0°C) within 24 hours prior to Visit 2 or a temperature (measured by temporal artery thermometer) greater than or equal to 100.4°F (38.0°C) at the time of Visit 2* *This may result in a temporary delay of Visit 2 and/or vaccination	X	X

8. Receipt of an antipyretic medication (acetaminophen or ibuprofen) within 24 hours prior to Visit 2* *This may result in a temporary delay of Visit 2 and/or vaccination	X	X
9. Parent(s)/LAR is planning to administer a prophylactic antipyretic or medication on the day of, and/or within 7 days following Visit 2* *This exclusion does not apply if the caretaker indicates he/she might administer antipyretics or analgesics after Visit 2 to reduce fever or pain	X	
10. Unable to receive an intramuscular injection in the thigh* * For example – a broken bone or cast for treatment of broken bone in a lower extremity, congenital anomaly in lower extremity precluding administration in the affected extremity or if deemed inappropriate by the study investigator	X	
11. Any condition deemed by the investigator to place the child at increased risk as a result of their participation in the study	X	

²If study team during the period of enrollment subsequent to Visit 2 becomes aware subject met exclusion meets the definition of a major violation

Procedural Violations

Visit 1

- Written informed consent not obtained
- Study eligibility not reviewed
- Temperature using the temporal artery thermometer not obtained
- Assigned study products administered prior to randomization
- Assigned study products not administered according to respective package insert specifications
- Study products received were not according to randomization assignment
- Study products not administered in thighs

Visit 2

- Visit 2 not done
- Study eligibility not reviewed
- Temperature using the temporal artery thermometer not obtained
- Assigned study product (IIV if in sequential group) not administered according to package insert specifications
- Study products received were not according to randomization assignment
- Concomitant vaccine/s administered
- Study product not administered in thighs

Interval Between Visits 1 and 2

- The protocol notes that the maximal interval between Visit 1 (Day 1) and Visit 2 (Day 15 (+7)) is 21 days. If Visit 2 occurs between Day 15 and Day 25, it will not be considered a major Protocol Violation.

Parental assessments

- Parents did not measure temperature using temporal artery method

Other Major Protocol Violations

- Vaccines administered during any point during study period but not at Visit 1 or Visit 2
 - Emergency response
 - For other reason
- Use of immunosuppressive steroid dose (i.e. ≥ 14 days of daily receipt of 20 mg or 2 mg/kg body weight of prednisone or equivalent.) or other immune-modifying drugs or immunosuppressants from Visit 1 through 8 days after Visit 2
